7 SUBJECT SELECTION

7.1 Study Population

Subjects with a diagnosis of end stage renal disease (ESRD) who meet the inclusion and exclusion criteria will be eligible for participation in this study. Subjects with all vascular access types are eligible for the study and may include catheters, grafts, and fistulas. Potential study candidates should be screened for eligibility according to the study inclusion and exclusion criteria.

7.2 Informed Consent

IMPORTANT: The Code of Federal Regulations requires that the consent form signed by the Subject must be dated at the time consent is given. Also, medical records must contain documentation that informed consent was obtained prior to participation in a study. (21 CFR Parts 50 and 812)

The Investigator may determine whether potential Subjects are interested in participating in an investigation, but shall not request the written informed consent of any Subject to participate, and shall not allow any Subject to participate before obtaining Institutional Review Board (IRB) and FDA approval. The consent process shall begin before care is altered beyond the scope of a routine comprehensive examination for the purpose of participating in this study.

All Subjects in this research study should be completely informed about the purpose, duration, and pertinent details of the study. The informed consent process must be documented using a written form that has been approved by the IRB and includes all *Basic Elements of Informed Consent* and pertinent *Additional Elements* (21 CFR Part 50.25).

The Investigator must keep the original signed copies of all consent forms in the Subject's medical records and provide a copy to each Subject.

Appendix A outlines the screening and enrollment process and illustrates the point where informed consent should be obtained.

7.3 Subject Privacy

In accordance with the Health Insurance Portability and Accountability Act of 1996 (HIPAA), all Subjects should be informed of potential uses and disclosures of their medical information for research purposes, and their rights to access information about them by covered entities. Each Investigator will follow the procedures for securing HIPAA compliance as directed by their respective IRB or Privacy Board, and to obtain written authorization to use and disclose Subject information for all clinical research and research involving questioning of the Subject's or

Subjects' physician(s). Per individual site procedures, this authorization may be included as part of the Subject informed consent form.

7.4 Inclusion Criteria

Subjects must meet **ALL** of the inclusion criteria to be enrolled in the study.

1. Subject has provided informed consent and has signed a Health Insurance Portability and Accountability Act of 1996 (HIPAA) compliant authorization statement.
2. Subject is at least 18 of age.
3. Subject has end stage renal disease (ESRD) adequately treated with thrice weekly dialysis.
4. Subject is currently stable on dialysis for at least 3months on an FMC 2008K machine and Qd of 500ml/min or higher with no change in the following dialysis prescription parameters over that time: Qb, Qd, Dialyzer, Time.
5. Subject has a baseline Kt/V of greater than 1.2.
6. Subject has a stable vascular access.
7. Subject reports time to recovery of more than 4 hours or a modified ESAS with at least 5 symptoms of which at least 2 are rated as moderate (rating of 4-6) or severe (rating of 7-10).

7.5 Exclusion Criteria

If **ANY** of the exclusion criteria are met, the Subject is excluded from the study.

1. Subject is unable to complete the questionnaires.
2. Subject is pregnant or planning to become pregnant
3. Subject is scheduled for a change in modality or expected kidney transplant in the next 3 months.
4. Any other documented condition that the Investigator feels would prevent the Subject from successful inclusion in the study.

7.6 Subject Discontinuation and Replacement

Every Subject should remain in the study until completion of the required follow-up period. Subjects may voluntarily withdraw from the study at any time with or without reason and it will not have any negative impact on subsequent treatment. Conceivable reasons for Subject discontinuation may include, but are not limited to, the following:

- **Subject Withdrawal:** Subject participation in this study is voluntary. The Subject may choose to discontinue participation at any time without loss of benefits or penalty.
- **Discontinuation:** Subject participation may be discontinued by the Subject or Investigator because of a kidney Transplantation, relocation to another dialysis center, treatment modality change, hospitalization or death.
- **Sponsor/Investigator Termination:** The Sponsor/ Investigator may terminate the Subject's participation without regard to the Subject's consent if the Sponsor/Investigator believes it is necessary.
- **Exclusion Criterion Discovered After Enrollment:** A small number of Subjects may be enrolled despite meeting an exclusion criteria due to timing of study required clinical procedures. This will be documented by the study personnel and will be considered a protocol deviation.

8 STUDY PROCEDURES AND DATA COLLECTION

8.1 Baseline Evaluation

Subjects will be asked for their response to the TTR question and a modified ESAS. Subjects meeting the inclusion and exclusion criteria, will be consented and enrolled into the study. Enrollees will be randomized to treatment Group 1 or 2. Enrollee caregivers will be asked to complete a KDQoL SF-36 regarding their perception of the Subject's overall health. Additionally, historical dialysis treatment information including hemodialysis prescription and any recent changes, baseline laboratory values including kinetics, temperature, height, weight, body mass index, vascular access type, presence or absence of diabetes mellitus, hypotension, ejection fraction, arrhythmia, high blood pressure, and any other co-morbid conditions considered relevant may also be collected where available. Any subjects of child-bearing potential will be given a pregnancy test to confirm negative results. Those subjects will also be utilizing medically acceptable means of contraception during the study period. Demographic information will be collected including age, gender, ethnicity and race. Dialysis related medications, laboratory values, blood pressure readings taken before, during and after dialysis treatments and adverse event data may also be collected if available.

8.2 Group 1

Subjects will undergo staff administered dialysis treatment 3 times/week for 8 weeks In-Center with prescription adjustments as outlined in the Schedule of Events. Subjects will respond to the TTR question and modified ESAS at the completion of every week. Caregivers will be asked to respond to the KDQoL SF-36 during week 4 and week 8. Subjects Serum Potassium, BUN, CO₂, Phos, Na, Beta-2-Microglobulin, Vitamin B12 and Kt/V labs and treatment flowsheets will also be evaluated. Dialysis prescription changes, dialysis related medications, blood pressure readings taken before, during and after dialysis treatments and adverse event data may also be collected if available. Group 1 will dialyze for the first 4 weeks of the study at a Qd of 300ml/min, then for the last 4 weeks at a Qd of 500ml/min.

8.3 Group 2

Subjects will undergo staff administered dialysis treatment 3 times/week for 8 weeks In-Center with prescription adjustment as outlined in the Schedule of Events. Subjects will respond to the TTR question and modified ESAS at the completion of every week. Caregivers will be asked to respond to the KDQoL SF-36 during week 4 and week 8. Subjects Serum Potassium, BUN, CO₂, Phos, Na, Beta-2-Microglobulin, Vitamin B12 and Kt/V labs and treatment flowsheets will also be evaluated. Dialysis prescription changes, dialysis related medications, blood pressure readings taken before, during and after dialysis treatments and adverse event data may also be collected if available. Group 2 will dialyze for the first 4 weeks of the study at a Qd of 500ml/min, then for the last 4 weeks at a Qd of 300ml/min.

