6 STUDY DESIGN

This is a single center, post market, prospective, single blind, randomized, cross-over study involving approximately 50 subjects currently dialyzing on a conventional dialysis machine at a dialysate flow rate of 500ml/min or higher thrice weekly. The study may collect retrospective and prospective medical records and other treatment data. Enrolled subjects will answer the question, "How long does it take you to recover from a dialysis session?" (TTR) along with a modified ESAS at baseline and weekly. Subjects will be screened prior to entry into the study and enrolled if time to recovery at baseline of > 4 hours or the results of their modified ESAS demonstrate at least 5 dialysis related symptoms with at least 2 being described as moderate (rating of 4-6) or severe (rating of 7-10). Caregivers of screened Subjects meeting the study criteria will be given a baseline KDQoL SF-36 to determine their perception of the Subject's current state of health. Subjects enrolled will be randomized to two groups. Group 1 will dialyze for the first 4 weeks of the study at a Qd of 300ml/min, then for the last 4 weeks at a Qd of 500ml/min. Group 2 will dialyze for the first 4 weeks of the study at a Qd of 500ml/min, then for the last 4 weeks at a Qd of 300ml/min. At the end of each week, the Subject will respond to the TTR question as well as the modified ESAS survey. Subject caregivers will complete the KDQoL at the end of each 4-week interval. The study will assess the Subject and Subject caregiver responses to the survey tools as well as other outcome measures which may include but are not limited to, kinetics, laboratory values, blood pressure measurement, intradialytic interventions, missed or shortened treatments, and/or changes to treatment parameters. The study will collect subject demographics and dialysis related medications. The goal is to enroll at least 15 Subjects who report intradialytic symptoms as the ITT group for study analysis.

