6.2 Evaluation of Safety

Treatment with a Qd of 300ml/min has been shown to be safe and effective in the treatment of ESRD subjects. It has also been demonstrated that dialysis at a Qd of 300ml/min can achieve the prescribed adequacy target of a Kt/v of 1.2 or greater. Standard safety precautions as per clinic protocol will be continued. No portion of this study will be beyond the standard of care.

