6.3 Blinding and Randomization

This study is a single center, post market, prospective, single blind, randomized, cross-over study comparing symptoms with a conventional dialysis device at a Qd of 500 ml/min and a Qd of 300 ml/min. Only Subjects will be blinded to the dialysis device Qd.

Subjects will be randomized to either arm at a 1:1 ratio using excel's RANDBETWEEN function. Subjects will be randomly assigned a 0 or a 1. Subjects that are assigned '0' will go to Group 1, and subjects that are assigned '1' will go to Group 2.

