10 ETHICAL CONSIDERATIONS

Risks: The risks to subjects participating in this study are minimal. Subjects will be informed of the potential risk of an overall decrease in weekly Kt/V due the change in Qd. A possible risk is exposure of protected health information. Every effort will be made to maintain subject privacy.

Benefits: The study will provide information on Subject self-reported symptoms in the real world setting for subjects who dialyze thrice weekly with a dialysate flow rate of 500ml/min who are changed to a dialysate flow

rate of 300ml/min. Pts will be informed of the potential benefits from none to possible reduction in symptoms from the potential intervention. Subjects and their caregivers will be compensated for their time and effort to complete the surveys as requested.

Participation in this study is voluntary. Failure to participate in the study will not impact Subject care.

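### Adverse-event collection is optional and unscheduled, so adverse-event rates cannot be reliably described or compared between the Qd 300 and Qd 500 periods

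*Protocol*

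**What the plan says.** Section 8.1 (baseline) states that "blood pressure readings taken before, during and after dialysis treatments and adverse event data may also be collected if available". Sections 8.2 (Group 1) and 8.3 (Group 2) use the same optional wording, "adverse event data may also be collected if available", for the eight treatment weeks. Appendix A lists the questionnaires, Kt/V, laboratory values, review of treatment records and interventions, and review of missed or shortened treatments. It has no row for adverse events.

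The flow rate is assigned by the study: "Group 1 will dialyze for the first 4 weeks of the study at a Qd of 300ml/min", then four weeks at 500 ml/min, with the reverse order in Group 2. Section 6.3 adds that "Only Subjects will be blinded to the dialysis device Qd". Section 10 says that "Subjects will be informed of the potential risk of an overall decrease in weekly Kt/V due the change in Qd".

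Section 6.2, on evaluation of safety, refers to earlier evidence for Qd 300 and says that "Standard safety precautions as per clinic protocol will be continued". It sets no rule for identifying, recording or reporting adverse events.

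**The concern.** The protocol is not silent on adverse events. It states a rule, and the rule lets the site record them or not, depending on what happens to be at hand. Under such a rule an absent record may mean that no event occurred or that nobody wrote it down, and the two cannot be told apart afterwards.

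That matters here because the staff who would do the recording know the flow rate. How much they record could depend on which rate is running, and then a table of events by Qd would partly reflect recording habits. The problem arises at collection, so no analysis plan can repair it.

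**Working it through.** The protocol gives no event rate or capture rate, and there is no figure to reproduce. The check is a comparison of what the protocol requires with what it leaves optional, followed by the direction of any bias.

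**Step 1. Required and optional data in the treatment weeks**

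| Item | Status | Where |
|---|---|---|
| Time to recovery, modified ESAS | Required weekly | 8.2, 8.3, Appendix A |
| Kt/V and serum chemistry | Required; Weeks 1 and 5 | 8.2, 8.3, Appendix A |
| Treatment flowsheets | Required | 8.2, 8.3 |
| Intradialytic interventions, with reason | Secondary endpoint; reviewed Weeks 9-12 | Synopsis, Appendix A |
| Missed or shortened treatments | Secondary endpoint; reviewed Weeks 9-12 | Synopsis, Appendix A |
| Adverse events | Optional, if available; no schedule row | 8.2, 8.3 |

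Within the same paragraphs of 8.2 and 8.3, questionnaires, laboratory values and flowsheets are stated with *will*, and adverse events with *may*. The optional status is therefore part of the rule as written. No other section makes collection mandatory.

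**Step 2. What the required items leave uncovered**

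- Interventions and shortened treatments concern the dialysis session. They do not require a record of what happens between sessions.
- Section 7.6 lists hospitalisation and death among possible reasons for discontinuation. A hospitalisation that does not end participation leaves no required record, and nothing requires the date or the Qd in use.
- A missed treatment may be the trace of an event, but the synopsis asks for a reason only for interventions.
- Kt/V and chemistry have one time point per Qd period, in its first week.

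**Step 3. Direction of any bias**

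Let c300 and c500 be the share of true events recorded in each period. Then

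recorded ratio (300 to 500) = true ratio × c300 / c500.

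Neither share can be obtained from the protocol. As an illustration only, assume a true risk of 20% in both periods and capture of 90% in one period and 60% in the other:

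- Recorded risks: 0.20 × 0.90 = 18% and 0.20 × 0.60 = 12%.
- Higher capture at Qd 300: 18 / 12 = 1.5.
- Higher capture at Qd 500: 12 / 18 = 0.67.
- Equal capture at 60%: the ratio is 1.0, but both periods show 12% against a true 20%, so the description is wrong even though the comparison is not.

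These values show that the sign is open; they do not estimate the bias in this trial. The cross-over does not remove it. Comparing each subject with themselves cancels stable differences between subjects in how readily events come to notice, but not a difference in capture tied to the flow rate.

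**The case against.** The strongest reply is that safety is not unmonitored and that comparative safety is not an aim. Interventions with their reasons, missed or reduced treatments, flowsheets, Kt/V and chemistry are planned in both periods. The one risk named in Section 10, a lower Kt/V, is measured in each. No objective or endpoint is comparative safety, Section 11 plans descriptive statistics only, and Section 5 commits the study to GCP and the applicable regulations.

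Much of this stands, and it limits the point. A reader might infer that the two periods cannot be compared for safety at all; the planned data contradict that, since they support a limited descriptive comparison. A reader might also count every planned session as lacking a safety record, but flowsheets are to be evaluated and interventions counted.

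Two further inferences are unsupported. One is that under-recording would occur at Qd 300 and make it look safer. Nothing in the protocol says so, and staff could equally record more at the newly assigned flow. The other is that Section 6.2, which says that "No portion of this study will be beyond the standard of care", contradicts Section 10, which discloses a "potential risk of an overall decrease in weekly Kt/V due the change in Qd". A prescription within standard care can still carry a disclosed risk, so the two statements can both be true.

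The reply does not remove the core. A general commitment to GCP does not override a specific sentence making collection optional, and a descriptive count of events by Qd carries the same weakness as a tested one.

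**Conclusion.** The point holds in a limited form. As written, the protocol does not secure adverse-event data, so adverse-event rates, including hospitalisations and deaths between sessions, cannot be reliably described or compared by Qd. This rests on the optional wording in Sections 8.1 to 8.3, the missing row in Appendix A, and the absence of any overriding requirement elsewhere in the protocol. The unblinded staff make differential recording possible; the protocol does not show that it would occur.

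The size cannot be stated: it depends on capture shares that the protocol does not give, and the direction is open. The conclusion concerns adverse events only and leaves the planned intervention, treatment, Kt/V and laboratory data intact. Since safety comparison is not a stated objective, this is a change that should be made; it does not undermine the primary endpoint.

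**What to change.** In Sections 8.2 and 8.3, take adverse events out of the optional list and state that adverse events, hospitalisations and deaths *will be recorded in the same way in both periods*, each with its date and the Qd in use. Add an adverse-event row to Appendix A for Weeks 1-8. Summarise the events descriptively by Qd in use, in keeping with Section 11.

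The cost is a modest amount of prospective data entry by site staff at treatments already being delivered. It should not be treated as covered by the Weeks 9-12 record review, because a later review finds only what was written down at the time. The change affects data collection only and leaves the assigned flow rates and clinical management as they are. Sections 6.2 and 10 need no reconciliation on this point.

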9 STUDY LIMITATIONS

Limitation of this include its small size and in a single center. Additionally, every attempt has been made to remove any variables other than change in dialysis treatment device; however, Subjects with ESRD have complex medical histories and the effect of illness unrelated to ESRD (whether worsened or improved) was not taken into consideration. Socioeconomic factors that can affect a Subject's sense of wellbeing or any changes to these factors during the study were also not accounted for.

10 ETHICAL CONSIDERATIONS

Risks: The risks to subjects participating in this study are minimal. Subjects will be informed of the potential risk of an overall decrease in weekly Kt/V due the change in Qd. A possible risk is exposure of protected health information. Every effort will be made to maintain subject privacy.

Benefits: The study will provide information on Subject self-reported symptoms in the real world setting for subjects who dialyze thrice weekly with a dialysate flow rate of 500ml/min who are changed to a dialysate flow

rate of 300ml/min. Pts will be informed of the potential benefits from none to possible reduction in symptoms from the potential intervention. Subjects and their caregivers will be compensated for their time and effort to complete the surveys as requested.

Participation in this study is voluntary. Failure to participate in the study will not impact Subject care.

11 STATISTICAL METHODS

Descriptive statistics will be performed. Data resulting from this study may be compared to prior studies evaluating the frequency of Subject reported symptoms.

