15 REFERENCES10

APPENDIX A: SCHEDULE OF ASSESSMENTS12

1 PROTOCOL SYNOPSIS

Title	A Post-Market, Single Blind, Randomized Clinical Prospective Study on Intradialytic Symptoms in Subjects treated with Qd 500 vs Qd 300
Study Goal	To determine the impact of dialysate flow rate (Qd) on Subject reported dialysis related symptoms and on time to recovery post dialysis.
Study Background	Subjects undergoing conventional intermittent thrice weekly hemodialysis using a Qd of 500ml/min or higher report many inter and intra dialytic symptoms. Common symptoms include fatigue, cramping, and insomnia. Subjects treated on the Tablo hemodialysis system report 'feeling better'. Tablo has a dialysate flow rate of 300 ml/min.
Study Objective	The objective of this study is to determine if Subjects who report dialysis symptoms while meeting adequacy (as determined by Kt/V of 1.2 or greater) on thrice weekly dialysis or who have a recovery time of at least 4 hours when treated on a conventional, i.e. non Tablo, hemodialysis device feel better with a reduced dialysate flow rate of 300ml/min based on an assessment of time to recovery post dialysis and Subject reported symptoms via a modified weekly ESAS survey.
Study Length	The study will last approximately 8 weeks consisting of chart review, Subject selection, medical record review, data collection and data analysis.
Inclusion Criteria	
 1. Subject has provided informed consent and has signed a Health Insurance Portability and Accountability Act of 1996 (HIPAA) compliant authorization statement. 2. Subject is at least 18 of age. 3. Subject has end stage renal disease (ESRD) adequately treated with thrice weekly dialysis. 4. Subject is currently stable on dialysis for at least 3 months on a conventional dialysis machine and Qd of 500ml/min or higher with no change in the following dialysis prescription parameters over that time: Qb, Qd, Dialyzer, Time. 5. Subject has a baseline Kt/V of greater than 1.2. 6. Subject has a stable vascular access. 7. Subject reports time to recovery of more than 4 hours or a modified ESAS with at least 5 symptoms of which at least 2 are rated as moderate (rating of 4-6) or severe (rating of 7-10).

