Exclusion Criteria	
 1. Subject is unable to complete the questionnaires. 2. Subject is pregnant or planning to become pregnant. 3. Subject is scheduled for a change in modality or expected kidney transplant in the next 3 months. 4. Any other documented condition that the Investigator feels would prevent the Subject from successful inclusion in the study.
Primary Endpoint	Change in time to recovery and self-reported symptoms.
Secondary Endpoint	Caregiver assessment of changes in Subject's health, missed or reduced treatments, number of intradialytic interventions (saline, prn medications, early discontinuation, UF change related to sxS) and the reason for intervention.

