3 BACKGROUND

Subjects experience various symptoms during hemodialysis. Prior studies have shown that fatigue, muscle cramps, insomnia and pruritis are most commonly reported as symptoms associated with dialysis⁽⁵⁾. The frequency and severity of intradialytic symptoms are associated with missed treatments, shortened treatment time and delayed time to recovery after dialysis^(3,7,8). Longer time to recovery has also been shown to be a simple, reproducible, tool associated with poorer HRQoL, hospitalization and mortality^(3,4). Subjects treating on the Tablo system have previously reported feeling better when dialyzing thrice weekly with this device. The Tablo system utilizes a dialysate flow rate of 300ml/min to achieve the standard adequacy target as defined as a Kt/V of 1.2 or greater^(1,9). To better understand the feeling better effect on Tablo, this study was designed to determine if a decrease in dialysate flow rate on a conventional dialysis device produces a similar effect on Subject reported symptoms. This study assesses time to recovery as well as prevalence and severity of Subject reported symptoms via a weekly modified Edmonton Symptom Assessment System when dialysate flow rate is decreased from 500ml/min or higher

to 300ml/min on standard thrice weekly dialysis. In addition, the Subject's primary caregiver will be given a KDQoL SF-36 to complete as to their perception of the Subject's quality of life at baseline as well as after each 4-week interval. These assessment tools have been shown to be reliable, simple methods for symptom assessment (2,4,8,10,11,12)

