4 STUDY OBJECTIVE

The objective of this study is to determine if Subjects who report dialysis symptoms while meeting adequacy (as determined by Kt/V of 1.2 or greater) on chronic thrice weekly dialysis or who have a recovery time of more than 4 hours when treated on a conventional, i.e. non Tablo, hemodialysis device feel better with a reduced dialysate flow rate of 300ml/min based on an assessment of time to recovery post dialysis, weekly modified ESAS, and Subject's caregiver assessment of the Subject's symptoms.

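### The primary endpoint does not say what change is measured from, and Section 11 does not tie it to the randomised Qd 300 versus Qd 500 contrast (free improvement)

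*Protocol*

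**What the plan says.** **Endpoint.** The Primary Endpoint row of the Protocol Synopsis is one phrase: "Change in time to recovery and self-reported symptoms". It does not say what the change is measured from or between, and no other section does.

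**Analysis.** Section 11 of the Protocol reads "Descriptive statistics will be performed. Data resulting from this study may be compared to prior studies evaluating the frequency of Subject reported symptoms". It mentions neither the two flow rates nor the cross-over.

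**Design.** The comparison of interest does appear elsewhere. The title refers to "Intradialytic Symptoms in Subjects treated with Qd 500 vs Qd 300". Section 6.3 describes a "cross-over study comparing symptoms with a conventional dialysis device at a Qd of 500 ml/min and a Qd of 300 ml/min". Section 6 gives both sequences, four weeks at each rate, with recovery time (TTR) and modified ESAS answered every week.

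**The move onto Qd 300.** Section 3 speaks of assessing outcomes "when dialysate flow rate is decreased from 500ml/min or higher" to 300 ml/min. The Benefits paragraph of Section 10 refers to "subjects who dialyze thrice weekly with a dialysate flow rate of 500ml/min who are changed to a dialysate flow" rate of 300 ml/min. Section 7.4, item 4, admits subjects on a "Qd of 500ml/min or higher with no change in the following dialysis prescription parameters over that time".

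**Baseline.** In Appendix A the only TTR and ESAS responses before study treatment are at Week -1. Under Section 6 and Section 7.4, item 7, entry requires a TTR above 4 hours or an ESAS meeting a symptom-count and severity rule.

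**The concern.** An endpoint defined as a change needs a reference. Two are open here: the on-study Qd 500 period, which the randomisation supplies, and the pre-study state recorded at Week -1.

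The second has two weaknesses. Subjects enter because a Week -1 score is high, so on average that score will be lower on retest whatever the flow rate. Also, Week -1 is not a fixed Qd 500 reference, because the pre-study prescription may be above 500 ml/min.

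If change from Week -1 were reported for Qd 300 without its Qd 500 counterpart, regression to the mean, or a different prior flow rate, could be read as a benefit of Qd 300. That would forgo the comparison for which subjects are randomised. The text as written does not rule it out.

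**Working it through.** The plan states no figure to reproduce. The check is a reading of the text, one identity, and an illustration of direction.

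**1. Which reference does the text support?**

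| Place in the Protocol | On-study 300 vs 500 | Change from pre-study state |
|---|---|---|
| Title; Section 6; Section 6.3 | Yes | No |
| Section 4 ("feel better with a reduced dialysate flow rate of 300ml/min based on an assessment of time to recovery post dialysis") | Fits | Fits |
| Section 3; Section 10, Benefits | Not stated | Suggested, but neither defines an endpoint |
| Primary Endpoint row | Allowed | Allowed |
| Section 11 | Allowed, not named | Allowed, not named |

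The design sections point to the on-study contrast. The two places that should fix it, the endpoint row and Section 11, do not.

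**2. What happens to the baseline?** Let B be the Week -1 score, and Y300 and Y500 a subject's summaries of the weekly scores at each rate. With complete data,

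(Y300 − B) − (Y500 − B) = Y300 − Y500.

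B cancels. Whatever selection or prior flow rate did to B affects both changes equally and leaves the contrast untouched. It matters only when Y300 − B is read without Y500 − B.

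**3. Direction of the one-sided change with no flow-rate effect.** All inputs are assumed; none is in the documents. Treat TTR and ESAS as standard normal scores Z1 and Z2 with correlation ρ. A subject enters if either exceeds a common cut-off, set so that a fraction P of screened subjects qualifies. With test-retest correlation r,

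expected fall from Week -1 = (1 − r) × E[Z1 | entered].

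- P = 0.3, ρ = 0.5: E = 0.943. At r = 0.5 the fall is 0.5 × 0.943 = 0.471 SD.
- P = 0.5, ρ = 0.35: E = 0.606. At r = 0.6 the fall is 0.4 × 0.606 = 0.242 SD.
- P = 0.7, ρ = 0.2: E = 0.351. At r = 0.8 the fall is 0.2 × 0.351 = 0.070 SD.
- P = 0.9, r = 0.8: about 0.03 SD.

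The sign is always an apparent improvement. The size runs from negligible to nearly half an SD depending on values that nobody can take from the protocol. Equal cut-offs on two normal scores are also a simplification of the actual ESAS rule. A simulation of the middle case gave −0.242 on Qd 300, −0.242 on Qd 500 and 0.000 for 300 minus 500, as the identity requires.

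**The case against.** The best defence is that the protocol, read whole, has one comparison in mind. The title, the study goal, the two sequences and Section 6.3 all set 300 against 500, and a randomised cross-over has little other purpose. Section 4 fits that reading as well as any other. Section 3 is background and Section 10 is an ethics paragraph that mentions 500 ml/min only, so neither defines an endpoint. Descriptive statistics can describe 300 against 500, the comparison with prior studies is optional, and the tables and model may be in a SAP that is not shown.

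Most of this stands. A reader might infer that the protocol never states the Qd 300 versus Qd 500 comparison; it does, in several places. A reader might also infer that the trial plans a before-and-after analysis, or that change from Week -1 is biased however it is used. No section proposes reporting Qd 300 alone, and when both rates are reported against the same baseline the bias cancels.

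What does not stand is that nothing needs changing. The reference of a primary endpoint belongs in the protocol. Here the word *Change* admits two quantities, and the only comparison named in Section 11 does not use the randomisation. A report of change from Week -1 on Qd 300 would comply with both passages.

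**Conclusion.** The point holds as a free improvement. The intended contrast can be inferred from the design sections, but the endpoint row and Section 11 do not commit to it.

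The risk is conditional: change from Week -1 misleads only if it is read for Qd 300 without the Qd 500 counterpart. In that case regression to the mean favours an apparent improvement, and for subjects previously above 500 ml/min the comparison is with another flow rate. Only the direction of the regression effect is claimed. The illustrative sizes rest wholly on assumed inputs and are not an estimate for this trial. The cancellation of the baseline rests on each subject having data at both rates.

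The use of a model, the handling of period, the ESAS summary and any exclusion of early weeks are ordinary SAP content, and their absence from the protocol is not criticised.

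**What to change.** In the Primary Endpoint row and in Section 11, state: *The primary result is the within-subject difference, Qd 300 minus on-study Qd 500, in TTR and in modified ESAS, from the scheduled weekly on-treatment responses, reported with a 95% confidence interval. Change from Week -1 and comparison with prior studies are supportive.*

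A confidence interval is compatible with a descriptive study; it shows how precisely the contrast is estimated and requires no hypothesis test. The model, period handling, ESAS summary and treatment of early weeks may stay in the SAP.

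The cost is wording. The weekly TTR and ESAS responses under both flow rates are already in Appendix A, so no data, visits or subjects are added, and no treatment rule changes.
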